#### Post-Trial Provisions

34. In advance of a clinical trial, sponsors, researchers and host country governments should make provisions for post-trial access for all participants who still need an intervention identified as beneficial in the trial. This information must also be disclosed to participants during the informed consent process.

#### Research Registration and Publication and Dissemination of Results

35. Every research study involving human subjects must be registered in a publicly accessible database before recruitment of the first subject.

36. Researchers, authors, sponsors, editors and publishers all have ethical obligations with regard to the publication and dissemination of the results of research. Researchers have a duty to make publicly available the results of their research on human subjects and are accountable for the completeness and accuracy of their reports. All parties should adhere to accepted guidelines for ethical reporting. Negative and inconclusive as well as positive results must be published or otherwise made publicly available. Sources of funding, institutional affiliations and conflicts of interest must be declared in the publication. Reports of research not in accordance with the principles of this Declaration should not be accepted for publication.

#### Unproven Interventions in Clinical Practice

37. In the treatment of an individual patient, where proven interventions do not exist or other known interventions have been ineffective, the physician, after seeking expert advice, with informed consent from the patient or a legally authorised representative, may use an unproven intervention if in the physician's judgement it offers hope of saving life, re-establishing health or alleviating suffering. This intervention should subsequently be made the object of research, designed to evaluate its safety and efficacy. In all cases, new information must be recorded and, where appropriate, made publicly available.

## 5. PATIENT DIARY

Visit data   .   .

Compilation instruction

Please from tomorrow for 14 days each day fill this diary.

In the first column insert the data, in the column from two to six put a cross at any Proctinus cream application.

If you take any drug note in the other drug column the name of each drug taken

In the general health column insert information if you have any different disease than hemoroides.

In the column note insert any other relevant information.

For any doubt on the diary filling please contact the doctor of this study

Dr. \_\_\_\_\_ contact number \_\_\_\_\_

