### **3. TIME PERIOD AND FREQUENCY FOR EVENT ASSESSMENT AND FOLLOW-UP**

The occurrence of an adverse event (AE) or serious adverse event (SAE) may come to the attention of study personnel during study visits and interviews of a study participant presenting for medical care. At each visit/assessment, the participant should be assessed for the possible occurrence of an AE/SAE. Care will be taken not to introduce bias when detecting adverse events and/or SAEs. Open-ended and non-leading verbal questioning of the participant is the preferred method to inquire about adverse event occurrences.

Any medical condition that is present at the time that the participant is screened will be considered a baseline and not reported as an AE. However, if the study participant's condition deteriorates at any time during the study, it will be recorded as an AE. Changes in the severity of an AE will be documented to allow an assessment of the duration of the event at each level of severity to be performed. AEs characterized as intermittent require documentation of the onset and duration of each episode.

AE/SAE can occur during any period of the study. The Investigator will record all reportable events with start dates occurring any time after informed consent is obtained until 7 (for non-serious AEs) or 30 days (for SAEs) after the last day of study participation. At each study visit, the investigator will inquire about the occurrence of AE/SAEs since the last visit. Each patient will receive a phone call from the investigator 30 days after the end of the study to check if there have been AEs. Events will be followed for outcome information until resolution or stabilization.

AE/SAE, as all medical occurrences, should be recorded by the Investigator in the subject's medical records as source data.

Each identified AE is assessed by the Investigator for Seriousness and Causality relationships to the Investigational Medical device or procedure.

All AE/SAE will be recorded on the appropriate case report form (CRF) by the Investigator.

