### 3.7.2.1. Study visits

#### Visit 1 Screening / Baseline Visit (day 0)

At each Centre, patients will be enrolled consecutively. During this visit, patients who will meet the eligibility criteria (inclusion and exclusion criteria) will be enrolled after the signature of the informed consent form and will be informed verbally and in writing about the nature and requirements of the trial. Patients agreeing with the participation in the study will have to date and sign the informed consent form prior to any study-related procedure. All the screening procedures must be completed during this visit.

During this visit, the Investigator will collect information regarding medical history, demography, concomitant treatments and medications, AE/SAE if applicable. The Investigator will report data on the appropriate eCRF pages.

A physical examination will be performed, including evaluations of vital signs; pulse, blood pressure (diastolic and systolic), weight / height and BMI (kg/m^2) data will be collected. An evaluation of the haemorrhoidal disease will be performed, and a confirmation of the diagnosis and of the stage of haemorrhoids will take place, according to inclusion criteria (patients diagnosed with Grade I – II symptomatic haemorrhoids (according to Goligher classification, confirmed by clinical and anoscopic or proctoscopic examination performed within 3 months before baseline)

During this visit the following questionnaires will have to be completed:

- **HR-QoL questionnaire: SHSHD (by patient)**
- **HSS (by Investigator)**
- **HDSS (by patient)**

During this visit, the MD will be provided to each patient. The used, partially used and unused containers of the MD will have to be brought back to the centre on the last study visit. The MD will be supplied in the same package available on the market, and with the same leaflet / IFU – Instructions for Use.

A patient diary will be supplied; it will have to be completed at home by patients for the whole duration of the study. A series of information will have to be collected related to the health status of the patient (not an exhaustive list): use of any treatment or OTC or prescribed medications (concomitant treatments and medications), start and stop dates and name/dosage of the product will be collected; AE/ADE/DD occurrence; self-administration of the MD (according to IFU and standard clinical practice).

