#### **Undesirable effects**

There are no known undesirable effects deriving from the use of OBIO4A004CPR, however:

- \* Do not use in the presence of hypersensitivity to any of the ingredients.
- \* If you have doubts, apply a small amount of the emulsion on the inside of the forearm. If irritable red spots appear, we advise you not to use the product.
- \* Inform your doctor or pharmacist of any undesirable effects or if symptoms persist.

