#### **Please note**

In case of persistent or recurrent complaints, you should always contact your physician.

Also in the case of worsening or when symptoms of inflammation, allergic reaction or infection occur consult a doctor.

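### The visible diary instructions do not prompt for the adverse events, device effects and device deficiencies that the protocol assigns to the diary, and the health column points away from haemorrhoid-related worsening

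*Combined protocol and SAP*

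**What the plan says.** **What the diary is meant to hold.** Protocol section 3.7.2.1 (Visit 1) lists what the patient records at home. Besides other treatments, the list includes "AE/ADE/DD occurrence; self-administration of the MD (according to IFU and standard clinical practice". On duration it says of the diary that "it will have to be completed at home by patients for the whole duration of the study".

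**What counts as an adverse event.** Section 3.6.2, item 3, treats conditions present at screening as baseline and then adds: "However, if the study participant's condition deteriorates at any time during the study, it will be recorded as an AE".

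**What patients are told to write.** The Patient Diary (section 5 of the combined document) opens with "Please from tomorrow for 14 days each day fill this diary". It then names entries for the date, each cream application, other drugs, general health and notes. The health instruction is "In the general health column insert information if you have any different disease than hemoroides". The last entry is open: "In the column note insert any other relevant information".

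**Other routes for safety data.** Section 3.6.2 prefers open, non-leading questioning by the investigator. Section 3.7.2.1 has safety collection at Visit 2, together with a physical and haemorrhoid examination, and again at the day-30 call. CRF section 9 asks once about any adverse event since consent, without restriction by disease.

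**What is reported.** The Summary states that no adverse event occurred, and its Discussion presents that absence as demonstrating good tolerability.

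**The concern.** The device is applied in and around the anus, so an unwanted local effect would appear where the disease already causes pain, itching and burning. The leaflet recognises this kind of event: "Also in the case of worsening or when symptoms of inflammation, allergic reaction or infection occur consult a doctor". A patient with more burning or bleeding after applying the cream may well regard it as haemorrhoids, and the health column asks about something else. Under section 3.6.2 the same change would be an adverse event.

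A daily diary reduces dependence on memory. If it does not ask for the events most relevant to a locally applied device, that benefit is lost for them. Safety is a stated objective and the report draws a firm conclusion from a count of zero, so how completely events were sought affects how that zero can be read.

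**Working it through.** There is no planned figure to reproduce. The check is a comparison of texts, followed by simple arithmetic on the reported zero.

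**1. Content.**

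| Item | Protocol 3.7.2.1 (diary) | Visible diary instructions |
|---|---|---|
| Device applications | Required | Prompted |
| Other drugs | Required | Prompted |
| Adverse events and device effects | Required | Not named; health column limited to diseases other than haemorrhoids |
| Device deficiencies | Required | Not named |
| Anything else | List is not exhaustive | Free note column |

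The CRF text has no field named for device deficiencies either, and its Visit 2 and call pages have no adverse-event item. The section 9 question carries that role.

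**2. Duration.** The diary covers 14 days and is collected at Visit 2 (day 14 ± 2). Section 3.7.2.1 asks for it over the whole study, and the Synopsis gives 30 days per patient. The Synopsis also lists diary maintenance at the day-30 call, after the diary has been handed in. Section 3.7.2.1 calls Visit 2 the end of the study when it describes collection. On that reading the 14 days would fit, but the Synopsis duration would not.

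**3. Exposure recorded under these instructions.** With 50 patients and a mean of 34.44 applications (Table 4):
- patient-days: 50 × 14 = 700
- applications: 50 × 34.44 = 1,722

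These describe exposure. They do not estimate missed events.

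**4. A sign that the record merits checking.** In Table 6 the minimum HDSS difference (Visit 1 minus Visit 2) is −2.00, so at least one patient's symptom score rose by 2 points. Whether this met the section 3.6.2 definition cannot be judged from the tables.

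**5. What 0/50 supports.** The exact two-sided 95% upper bound is 1 − 0.025^(1/50) = 0.0711, or 7.1%.

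Suppose each affected patient is recorded independently with probability s. The bound on the true rate is then 0.0711/s. The documents give no value of s, so the values below 100% are assumptions:

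| Assumed capture s | Upper bound on true rate | Chance of recording 0/50 if true rate is 5%: (1 − 0.05s)^50 |
|---|---|---|
| 100% | 7.1% | 7.7% |
| 75% | 9.5% | 14.8% |
| 50% | 14.2% | 28.2% |
| 25% | 28.4% | 53.3% |

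**The case against.** The strongest reply is that the diary is neither the safety record nor the main source for it. Investigators ask open questions, examine the patient at Visit 2 and telephone at day 30, and the CRF question is unrestricted. Local symptoms are also scored at both visits: the HDSS covers pain, itching, bleeding, soiling and prolapse, and the HSS covers bleeding and thrombosis. The worse HDSS was itself captured at Visit 2 without the diary. The leaflet supplied with the device tells patients to see a doctor about worsening or allergic reaction. All of this stands. A reader might infer that local events were filtered out of the safety record, or that only recall at Visit 2 remained. The documents support neither.

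Nor were patients told to report other diseases only. The note column is open, and a rash could reasonably be entered as a different disease.

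Two limits on the evidence also stand. The diary grid is not in the text available, so the missing prompt is confirmed for the instructions alone. Section 3.7.2.1 says the diary will mention the follow-up call, which the visible text does not, so that text may be incomplete. Study documents were also to be prepared in Romanian, and the wording patients read is not shown.

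Finally, the leaflet sentence "If irritable red spots appear, we advise you not to use the product" concerns a trial application on the forearm. It is not evidence about reactions at the treated site.

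The reply leaves the mismatch in place: the protocol gives the diary a task that its visible instructions do not carry out.

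**Conclusion.** The point holds as a mismatch between protocol and diary, with a resulting risk of under-capture in one safety source. Section 3.7.2.1 assigns adverse events, device effects and device deficiencies to the diary. The visible instructions prompt for none of them, and the health column is worded away from the disease whose worsening section 3.6.2 counts as an adverse event. Duration also needs reconciling.

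The number of missed events cannot be derived, and it may be zero. A reader might take the zero count as a product of the diary. The documents allow only that incomplete capture is possible. What can be sized is the claim itself: even with full capture, 0/50 is compatible with a true rate of up to 7.1%, so it does not demonstrate good tolerability. The weaker bounds rest on assumed capture rates.

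The conclusion assumes that the grid and the Romanian version add no adverse-event prompt. Either could be checked quickly and would narrow the point.

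**What to change.** **Diary.** Replace the general-health instruction with one open, non-leading prompt, such as: *Write any new health problem or any symptom that got worse, including in the treated area, and any problem with the product, with start and stop dates.* This covers device deficiencies as well and lists no symptoms, in keeping with the preference in section 3.6.2.

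**Protocol.** Reconcile section 3.7.2.1 with the diary on content and on duration (whole study or 14 days).

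**Completed trial.**
- Re-read the drug, health and note columns of the 50 diaries for events not entered in the CRF.
- Have the investigator assess whether the patient or patients with a worse HDSS met the section 3.6.2 definition.
- State in the safety section that the diary instructions did not prompt for adverse events or device deficiencies.
- Replace the claim that the absence of events demonstrates tolerability with 0/50 reported and its exact two-sided 95% upper bound of 7.1%, noting that incomplete capture would weaken it. If the re-read finds events, update the count and the bound.

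**Cost.** One diary sentence, a protocol clarification, a review of 50 short diaries and a few lines of report text. The small downside is that some ordinary disease fluctuation will be entered and will need investigator assessment.

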## 6. CRF

Patient code

				
----------------------	----------------------	----------------------	----------------------	----------------------

### CASE REPORT FORM

#### STUDY TITLE

**Post-Marketing Clinical Follow-Up trial to evaluate the performance and safety of the medical device PROCTOeze® PLUS in the relief of haemorrhoidal disease and anal irritation symptoms**

### 1. INVESTIGATOR

--

### 2. CENTRE & PATIENT CODES

Site code	Patient code
 	    

### 3. INCLUSION EXCLUSION CRITERIA

#### 3.1. INFORMED CONSENT

Has the subject freely signed the written informed consent?	Yes  No 
---	--

Please note:

written informed consent must be given before any study specific procedures take place.

#### 3.2. INCLUSION CRITERIA

1	Patients diagnosed with Grade I - II symptomatic haemorrhoids (according to Goligher classification) confirmed by clinical and anoscopic or proctoscopic examination performed within 3 months before baseline.	Yes  No 
2	Patient ≥ 18 years old	Yes  No 
3	Patients able to do self-administration at home of the MD to treat symptoms of haemorrhoids and anal irritation.	Yes  No 
4	Patient free from the following treatments for haemorrhoids for at least 4 weeks: laser treatments for haemorrhoids, steroidal or non-steroidal anti-inflammatory drugs, analgesics, any anti-haemorrhoidal treatment, anticoagulants, and antiplatelet agents	Yes  No 
5	Patients able to communicate adequately with the Investigator and understand the trial questionnaire.	
6	Patients able to understand and who can provide valid informed consent to the trial.	

### 3.3. EXCLUSION CRITERIA

1	Inflammatory and infectious disease of the digestive tract (e.g., IBD – Inflammatory Bowel Disease).	Yes  No 
2	Frequent hemorrhoidal bleeding	Yes  No 
3	Severe, uncontrolled hypertension, renal failure, cirrhosis, colorectal cancer, anal fissure or fistula.	Yes  No 
4	Patients with any other medical condition that, in the opinion of the Investigator, would compromise participation or be likely to lead to hospitalisation during the study.	Yes  No 
5	Vulnerable patient: a patient who is or may be for any reason unable to take care of him or herself, or unable to protect him or herself against significant harm or exploitation	Yes  No 
6	Simultaneous involvement in any other research project	Yes  No 

If any criteria are ticked yes the patient is not eligible for the study

### 3.4. PATIENT'S CONFIRMATION ADMISSION

Has the patient been included in the study ?

**Yes  No**

Note

**4. VISIT 1 DATE**

d	d	m	m	y	y	y	y
---	---	---	---	---	---	---	---

**5. PATIENT'S CHARACTERISTICS AND PROCEDURE**

AGE _____	M  F 
Physical examination	 Yes  No
Vital signs 	 Yes  No
Medical History	 Yes  No
Short Health Scale for Haemorrhoidal Disease (SHS HD ) (by patient) filled	 Yes  No
Haemorrhoid Severity Score (HSS) (by Investigator)	 Yes  No
Haemorrhoidal Disease Symptom Score (HDSS) (by patient)	 Yes  No
Patient Diary supply	 Yes  No
MD supply	 Yes  No
other	 Yes  No  N/A

Concomitant medication		
	No	
	yes	Please specify
	9=unknown	

## 6. VISIT 2 DATE

d	d	m	m	y	y	y	y
---	---	---	---	---	---	---	---

Physical examination	 Yes	 No
Vital signs 	 Yes	 No
Medical History	 Yes	 No
Short Health Scale for Haemorrhoidal Disease (SHS HD ) (by patient) filled	 Yes	 No
Haemorrhoid Severity Score (HSS) (by Investigator)	 Yes	 No
Haemorrhoidal Disease Symptom Score (HDSS) (by patient)	 Yes	 No
Patient Diary collection	 Yes	 No
MD collection	 Yes	 No
other	 Yes	 No
	 N/A	

### Concomitant medication

	No
	yes      Please specify
	9=unknown

**7. VISIT 3 DATE (CALL VISIT)**

d	d	m	m	y	y	y	y
---	---	---	---	---	---	---	---

Physical examination	 Yes	 No
Vital signs 	 Yes	 No
Medical History	 Yes	 No
Short Health Scale for Haemorrhoidal Disease (SHS HD ) (by patient) filled	 Yes	 No
Haemorrhoid Severity Score (HSS) (by Investigator)	 Yes	 No
Haemorrhoidal Disease Symptom Score (HDSS) (by patient)	 Yes	 No
Patient Diary collection	 Yes	 No
MD collection	 Yes	 No
other	 Yes	 No
	 N/A	

**Concomitant medication**

	No
	yes      Please specify
	9=unknown

## 8. END OF STUDY

Please mark **only the primary reason**. Reasons other than **Study Completed** require explanation

- 1  Study completed
- 2  AE/SAE (complete AE & SAE form, if applicable)
- 3  Non-compliant participant
- 4  Withdraw consent
- 5  Failure to meet inclusion/exclusion criteria
- 6  Other

Explanation

*I am confident that the information supplied in this case record form is complete and accurate data. I confirm that the study was conducted in accordance with the protocol and any protocol amendments and that written informed consent was obtained prior to the study.*

Investigator's Signature:

Date of signature:

d	d	m	m	y	y	y	y
---	---	---	---	---	---	---	---

Note

**9. ADVERSE EVENTS**

Has the patient experienced any Adverse Events since signing the Informed Consent?								 Yes, specify below	 No	
AE no.	Adverse Event (diagnosis (if known) or signs/symptoms)	Start Date dd/mm/yyyy and Time (24 hour clock)	Stop Date dd/mm/yyyy and Time (24 hour clock)	Outcome 1=Recovered 2=Recovered with sequelae 3=Continuing 4=Patient Died 5=Change in AE 6=unknown	Severity 1=Mild 2=Moderate 3=Severe	Plausible relationship to the Study	Action taken with Study Drug 1=None 2=Dose Reduction Temporarily 3=Dose Reduced 4=Discontinued Temporarily 5=Discontinued	Withdrawn due to AE?	Serious AE (SAE)?	If SAE does it require immediate reporting?
1						 Yes  No		 Yes  No	 Yes  No	 Yes  No
2						 Yes  No		 Yes  No	 Yes  No	 Yes  No
3						 Yes  No		 Yes  No	 Yes  No	 Yes  No

In case complete the CIOMS form.

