Results	
Demographics and Baseline Characteristics
 
 
Number of Patients: 50
 
Gender Distribution 68% female, 32% male
 
Mean Age Approximately 50 years (SD 13.90) with no significant difference between genders (see Table 1 ).
 
 
Outcome Assessments
 
SHSHD
 
 
Baseline: 14.04 (SD 7.79)
 
End-of-Treatment: 7.80 (SD 3.69)
 
Mean Reduction: 6.24 points (P < 0.0001) (See Table 5 and Figure 2 for detailed analysis.)
 
 
HDSS
 
 
Baseline: 10.12 (SD 3.60)
 
End-of-Treatment: 7.20 (SD 2.47)
 
Mean Reduction: 2.92 points (P < 0.0001) (See Table 6 and Figure 3 for detailed analysis.)
 
 
HSS
 
 
Baseline: 8.50 (SD 2.11)
 
End-of-Treatment: 6.48 (SD 2.17)
 
Mean Reduction: 2.02 points (P < 0.0001)
 
A significant Visit x Gender interaction was found (P = 0.0272). (See Table 7 and Figure 4 for detailed analysis.)
 
 
Device Usage
 
Patient diaries indicated a mean usage of approximately 34 cream applications over the 14-day monitoring period, with daily consumption remaining relatively consistent and a slight decrease observed in the later study days.
 
Safety
 
No serious adverse events (SAEs) were reported. No, AE was reported.
										
Conclusions	
This post-marketing clinical investigation demonstrates that PROCTOeze® PLUS is effective in improving quality of life and reducing the symptoms associated with hemorrhoidal disease and anal irritation in adult patients with Grade I-II hemorrhoids.
 
The significant reductions in SHSHD, HDSS, and HSS scores (all P < 0.0001), combined with an acceptable safety profile, support the continued clinical use of PROCTOeze® PLUS.
 
Ongoing post-marketing surveillance is recommended to further confirm the long-term safety of the device.
										

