##### safety outcome

- Evaluation of AE, SAE, ADE, SADE, ASADE, USADE incidence assessed by Investigator and reported according to the current legislation for the whole study period. Device Deficiencies (DD) will be also evaluated.

The HS is a physician-reported measurement instrument based on PNR-Bleed classification, that classifies and describes the haemorrhoids based on the four main characteristics of the hemorrhoidal disease i.e., the degree of hemorrhoidal Prolapse (P), Number (N) of the primary hemorrhoidal columns involved, Relation (R) of the haemorrhoidal tissue to the dentate line and the amount of Bleeding (B) from it. All four components in this classification system are graded into five grades ranging from 1 to 5. Grade 1 is the normal anal cushions and Grade 5 is the worst grade in a specific characteristic. HSS is the total score obtained by the sum of the numerical grades of all four characteristics of haemorrhoids in the PNR-Bleed classification. The minimum HSS score is 4 and the maximum score can be 20. The HSS score of a normal person without any signs and symptoms of haemorrhoids is 4. Calculation of the HSS help in the quantification of the haemorrhoidal disease for further reference and is helpful in post-treatment patient follow-up to grade the response to treatment and to assess the effectiveness or failure of any particular treatment regimen for haemorrhoids. It may also be used in predicting and diagnosing the recurrence after any form of treatment for the haemorrhoids.

- The Haemorrhoidal Disease Symptom Score (HDSS) (Annex 3 “Collected variables”) (5,19) is a patient-reported outcome. The questionnaire will be administered by Investigator to each patient at baseline and on day 30, at the end of the treatment with the MD.

The HDSS is a patient-reported measurement instrument. It comprises five items. Symptoms are assessed using the patient-reported frequency of the 5 symptoms, including pain, itching, bleeding, soiling, and prolapse. Patients are instructed to answer based on their experience during the previous period. Each symptom is graded on a 5-point scale (0 = never, 1 = less than once a month, 2 = less than once a week, 3 = 1–6 days per week, 4 = every day or always), giving a total score ranging from 0 to 20.

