##### **2. CAUSALITY ASSESSMENT**

The Investigator will be responsible for assessing the causal relationship of the AE.

The relationship between the use of the medical device (including the medical-surgical procedure) and the occurrence of each adverse event shall be assessed and categorized.

The investigators (and the Sponsor) will use the following definitions to assess the relationship of the serious adverse event to the investigational device, the comparator or the investigation procedure.

Each SAE will be classified according to four different levels of causality:

1. Not related
2. Possible
3. Probable
4. Causal relationship

The sponsor and the investigators will use the following definitions to assess the relationship of the serious adverse event to the investigational device, the comparator or the investigation procedure:

1. Not related: Relationship to the device, comparator or procedures can be excluded when:

- the event has no temporal relationship with the use of the investigational device, or the procedures related to the application of the investigational device;
- the serious adverse event does not follow a known response pattern to the medical device (if the response pattern is previously known) and is biologically implausible;

- the discontinuation of medical device application or the reduction of the level of activation/exposure - when clinically feasible - and reintroduction of its use (or increase of the level of activation/exposure), do not impact on the serious adverse event;
- the event involves a body-site or an organ that cannot be affected by the device or procedure;
- the serious adverse event can be attributed to another cause (e.g., an underlying or concurrent illness/ clinical condition, an effect of another device, drug, treatment or other risk factors);
- the event does not depend on a false result given by the investigational device used for diagnosis, when applicable;

In order to establish the non-relatedness, not all the criteria listed above might be met at the same time, depending on the type of device/procedures and the serious adverse event.

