2. Possible: The relationship with the use of the investigational device or comparator, or the relationship with procedures, is weak but cannot be ruled out completely. Alternative causes are also possible (e.g., an underlying or concurrent illness/ clinical condition or/and an effect of another device, drug or treatment). Cases where relatedness cannot be assessed, or no information has been obtained should also be classified as possible.

3. Probable: The relationship with the use of the investigational device or comparator, or the relationship with procedures, seems relevant and/or the event cannot be reasonably explained by another cause.

4. Causal relationship: the serious adverse event is associated with the investigational device, comparator or with procedures beyond reasonable doubt when:

- the event is a known side effect of the product category the device belongs to or of similar devices and procedures;
- the event has a temporal relationship with investigational device use/application or procedures;
- the event involves a body-site or organ that
  - the investigational device or procedures are applied to;
  - the investigational device or procedures have an effect on;
- the serious adverse event follows a known response pattern to the medical device (if the response pattern is previously known);
- the discontinuation of medical device application (or reduction of the level of activation/exposure) and reintroduction of its use (or increase of the level of activation/exposure), impact on the serious adverse event (when clinically feasible);
- other possible causes (e.g., an underlying or concurrent illness/ clinical condition or/and an effect of another device, drug or treatment) have been adequately ruled out;
- harm to the subject is due to error in use;
- the event depends on a false result given by the investigational device used for diagnosis, when applicable;

In order to establish the relatedness, not all the criteria listed above might be met at the same time, depending on the type of device/procedures and the serious adverse event.

Only causality level 1 (i.e., "not related") is excluded from reporting. If either the sponsor or the investigator has assigned a higher causality level than "not related", the event should be reported.

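### Device deficiencies are a stated safety outcome that no CRF page or diary instruction asks about, and the CRF ties adverse-event causality to the study instead of the device or procedure

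*Combined protocol and SAP*

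**What the plan says.** Protocol section 3.5.1, under the safety outcome, lists "Evaluation of AE, SAE, ADE, SADE, ASADE, USADE incidence assessed by Investigator and reported according to the current legislation for the whole study period" and adds: "Device Deficiencies (DD) will be also evaluated". The Schedule of Assessments (synopsis and section 3.7.2) marks the AE/ADE/DD assessment at Visit 1, Visit 2 and the follow-up call. Section 3.7.2.1 repeats it for Visit 2 and makes it the only listed task of the call. For Visit 1, the same section says the diary will gather occurrences of AEs, ADEs and device deficiencies.

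On causality, section 3.6.1 defines an ADE by its relation to use of the device. Section 3.6.2 (2) requires the relationship between device use, including the procedure, and each adverse event to be categorised. It then says: "Each SAE will be classified according to four different levels of causality". Section 3.6.2 (3) requires every AE to be assessed for causality to the device or procedure and recorded on the CRF.

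The CRF adverse-event page (CRF section 9) has a yes/no column headed "Plausible relationship to the Study", a yes/no column for seriousness, and one more for serious events: "If SAE does it require immediate reporting". The Results part of the Summary reports no SAEs and states: "No, AE was reported".

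**The concern.** A stated outcome needs a place where it is asked and recorded. For device deficiencies the protocol names the outcome and the contacts, but the forms do not carry the question. A blank then cannot be told apart from a question never put, so no count, denominator or rate can be given.

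For causality, the form asks about a different object from the one in the ADE definition. An investigator could tick yes for an event tied to a study visit and no for one tied to the emulsion, or the reverse, and an analyst could not tell which was meant.

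At stake is the safety half of the objective. The Summary concludes that the safety profile is acceptable, but one component of the safety outcome has no result behind it.

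**Working it through.** The documents give no figure to reproduce on this point. The check compares what the protocol requires with what the forms can hold.

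**1. Device deficiencies**

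| Where the protocol places them | What the form contains |
|---|---|
| Visit 1 (Schedule) | CRF section 5: no item |
| Visit 2 (Schedule, 3.7.2.1) | CRF section 6: no item |
| Call (Schedule, 3.7.2.1) | CRF section 7: no item; the page carries boxes for examination, vital signs and device collection |
| Any contact | CRF section 9 (adverse events): no column |
| Diary (3.7.2.1) | Diary instructions: date, applications, other drugs, other diseases, free note |

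The only places where a deficiency could appear are unstructured: the CRF *other* and *Note* entries and the diary note column. The diary grid itself cannot be seen in the text, but its column-by-column instructions can, and none names deficiencies.

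**2. Does zero AEs settle it?** No. Section 3.6.1 defines a deficiency as an inadequacy of the device, including malfunction, use error or inadequate manufacturer information. None of these requires an untoward medical event. The instructions for use have the patient pierce a seal and screw on a reusable applicator, so handling problems without an AE are conceivable.

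**3. Is a result reported?** The Executive summary, Results and Discussion give none, and the Statistical Analysis section contains no safety table.

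**4. The seven safety categories**

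| Category | Source as documented |
|---|---|
| AE | CRF section 9 |
| SAE | CRF section 9 |
| ADE, non-serious | Yes/no box on relation to the study; no other form is described as taking its causality |
| SADE | Not from the CRF page alone; SAE/SADE Reporting Form plus sponsor causality assessment (3.6.2 (4)) |
| ASADE, USADE | As for SADE, with the sponsor's expectedness assessment read against the risk analysis report (3.6.1) |
| Device deficiency | No field |

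**5. What the reported data imply.** ADE, SADE, ASADE and USADE are all subsets of AE. With 0 AEs in 50 patients, each of these counts is also 0. For scale, the exact upper limits on the per-patient AE rate for 0/50 are:

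- one-sided 95%: 1 − 0.05^(1/50) = 1 − 0.9418 = 5.8%
- two-sided 95%: 1 − 0.025^(1/50) = 1 − 0.9289 = 7.1%

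These describe AEs only. They do not measure the effect of the form layout. No such limit exists for device deficiencies, because neither a count nor the number of patients asked is known.

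**The case against.** The strongest reply is that the CRF is not the only safety record. Section 3.6.2 (4) sends every SAE to the sponsor on a dedicated form within 24 hours, and the sponsor assesses seriousness, expectedness and causality. The CRF also points to an AE and SAE form and a CIOMS form. This stands. A reader might infer that ASADE and USADE cannot be derived at all, and the documents do not support that. The serious-event form is not included, so its fields cannot be presumed missing.

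A reader might also infer that the yes/no box causes under-reporting, because section 3.6.2 (2) says: "Cases where relatedness cannot be assessed, or no information has been obtained should also be classified as possible". The documents do not support this either. The four levels and the reporting rule are written for serious events. Nothing makes the SAE report depend on the CRF box, and an event is reportable if either the sponsor or the investigator rates it above not related.

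A third reply is that, in a single-arm trial with one device, relation to the study is only loose wording. Annex 4 also puts device- and procedure-related events in one column. This stands in part: separate device and procedure columns are not needed. The box still does not ask what sections 3.6.1 and 3.6.2 require for each AE.

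Finally, treatment has ended and no AEs were reported, so the causality wording changed no reported count. That is correct. It does not answer the device-deficiency gap.

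**Conclusion.** The concern holds in two parts. First, device deficiency is a stated outcome with three scheduled assessments and a promised diary entry, but it has no structured field and no reported result. This is the live gap in the completed trial. Second, the CRF causality box does not match the protocol's definition of an ADE, so a non-serious ADE would not be recorded as defined. Here that is a defect of the form, with no effect on counts, because no AEs were reported.

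It does not follow that deficiencies occurred and were missed. The documents show only that the forms did not ask. Nor can the diaries be expected to fill the gap on their own: the protocol said they would collect deficiencies, but the instructions given to patients never asked for them.

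The conclusion assumes that the diary instructions cover all its columns and that no separate deficiency form exists. None is mentioned. The change is worth making because it is cheap and lets the trial answer an outcome it declared.

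**What to change.** **Forms (for any reuse).** Add an item to the CRF at Visit 2 and at the call: device deficiency, yes or no, describe. The device is first handed over at Visit 1, so the two later contacts are the informative ones. Add a matching diary column, as section 3.7.2.1 promises. Replace the yes/no relationship box with relationship to the device or procedure on the protocol's four levels. The protocol prescribes those levels for SAEs, but it requires categorisation for every AE and offers no other scale. The cost is one reworded column, one question at two contacts and one diary column, with no new procedures or staff.

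**This trial.** Treatment ended on 16 January 2025, so form changes cannot help it. Check the diary note column, the CRF *other* and *Note* entries and any returned-device records for the 50 patients. Report the device-deficiency count with its source. If these records cannot support a count, state that deficiencies were not systematically collected, and limit the safety conclusion to adverse events. The cost is one pass through existing records and a short addition to the report.
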